taVNS And N-Acetylcysteine For Oromotor Rehabilitation In Infants Of Diabetic Mothers

NAC + taVNS in IDM Who Are Poor Oral Feeders

NCT 04632069

8.10.21

taVNS and N-Acetylcysteine for Oromotor Rehabilitation in Infants of Diabetic Mothers

PROTOCOL TITLE:

taVNS and N-Acetylcysteine for Oromotor Rehabilitation in Infants of Diabetic Mothers

PRINCIPAL INVESTIGATOR:

[name]; [contact]

Study Endpoints (if applicable)

- **Primary outcome variables:** Daily po feeding volumes, comparing volumes before taVNS, to volumes during treatment within group, and comparing slopes of change in feeding volume during treatment between cohorts. We will also compare categorical number of infants who achieve full oral feeds and avoid a G-tube in this group compared to our prior IDM cohort who only received taVNS and were largely non-responders (8/9).
- **Secondary outcomes:** Increase in [GSH] in BG by MRS before and after 3-4 days of NAC; Change in MRS metabolites and DKI metrics in EC, CC, IFOF, PTR, before and after NAC+taVNS treatment.
- **Safety Outcomes:** Gastric intolerance/emesis; bradycardia with taVNS (HR <80bpm for 5 seconds)

Inclusion and Exclusion Criteria/ Study Population

Inclusion Criteria: Infants of diabetic mothers who are failing oral feeding, >39 weeks gestation at enrollment, who are clinically stable, on minimal respiratory support (nasal cannula or room air), and clinical team has determined are G-tube candidates. We will include any IDM infant failing oral feeds, without a designated HgbA1c, as glucose control during pregnancy may be unknown in some infants transferred into tertiary care centers. *Thus, we are using the same entry criteria we will employ in a phase II clinical trial.*

Exclusion Criteria:

- 1) Unstable infants or those requiring respiratory support involving positive pressure.
- 2) Infants <39 weeks gestation at enrollment.
- 3) Major unrepaired congenital anomalies or anomalies that limit feeding volumes
- 4) Infants with cardiomyopathy
- 5) Repeated episodes of autonomic instability (apnea or bradycardia) which are not self resolving *
- 6) Inability or unwillingness of subject or legal guardian/representative to give informed consent

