*Preterm infants commonly have short periods of shallow or absent breathing or lower heart rate termed apnea and bradycardia, respectively, and most are being treated for these physiologic manifestations of prematurity with caffeine, an effective central stimulant. Infants are on cardiorespiratory monitors through the nursery stay with recording devices to capture events and play them back. However, nearly all of these events are self-resolving, meaning the infant resolves the breathing pause or bradycardia on their own. Infants who require repeated episodes of stimulation to come out of these events are defined as *unstable*. Similarly, infants on significant respiratory support with continuous positive airway pressure (CPAP) device or other form of high respiratory support are not stable enough for oral feeding, and receive only oral stimulation.

Congenital syndromes may be included if the infants do not have major, unrepaired anomalies or anomalies that limit feeding volumes.

We will enroll all IDMs who qualify and whose parents consent to the study including all racial and ethnic groups. We will only enroll neonates and infants of diabetic mothers as this is the group under study and are trying to avoid a G-tube.

Number of Subjects

We will enroll 10 infants of diabetic mothers who are failing oral feeding and have been determined likely to need a G-tube.

Prospective participants will be identified by the PI ([name]) at the Shawn Jenkins Children's Hospital (SJCH) neonatal intensive care units and checked for potential inclusion.

Data Management

Statistical analysis and power analysis: The purpose of this pilot is to determine the effect size, if any, of adding NAC to taVNS, in order to inform our planned R01 clinical trial application. Our proposed sample of 10 IDM infants would allow us to detect moderate effects on the following outcomes due to adding NAC.

1. **Increase in daily po feeding volumes:** Our existing IDM cohort (n=9) had increase of 1.3 ± 1.7 ml/kg/d over 10 days before taVNS, vs 7.0ml/kg/d during taVNS in responders (including the 1 IDM responder). Even with this small sample, 4 IDM responders would allow us to detect a significant difference between prior to and during NAC+taVNS (power 80%, $\alpha = 0.05$, paired t-test).

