2. **Number of IDM achieving full oral feeds:** If 6 out of 10 IDMs achieve full oral feeds with NAC+taVNS, we will determine a significant difference in response rate vs taVNS alone (1/9 responders) by χ^2 analysis.

Detailed Management Protocol

1. After obtaining consent, a **baseline MRS** will be obtained prior to starting NAC, along with a **baseline (0.5ml) heelstick blood sample in EDTA tubes**.
2. NAC will be started at **75 or 100 mg/kg/dose n.g. q 6h, administered 1h before a feed, for a total of 14 days**. *All infants have existing n.g. tubes for administering the remaining volume of the feed not taken by mouth. We will monitor for emesis with n.g. NAC administration.*
3. We will follow the clinical practice, based on USP 795 standards for non-sterile preparations (i.e., a 14 day beyond-use date). IDS will dispense a 24-hour supply in 4 unit dose syringes and the patient's **bedside nurse will dilute the dose with sterile water 1:3 prior to NG administration. A sterile water flush of 1ml will be given before and after the NAC dose to clear the n.g. tube.**
4. If frequent emesis accompanies NAC ng administration, we will dilute in a greater volume of saline (1:4) and hold a dose to make sure emesis is not due to NAC, but due to some underlying condition such as gastroesophageal reflux
5. After 3-4 days of NAC administration, a **second MRS** will be **obtained within 2hours after a NAC dose**. MRS will be performed without sedation, after a feed with MedVac® swaddling to induce sleep, as per our usual clinical protocol.
6. Blood samples (0.5ml) will be obtained by heelstick before, 1h, 2h and 4h after the NAC dose by heelstick for pharmacokinetic studies, timed around the NAC dose immediately before the MRS scan. Specimens will be stored in the locked Shawn Jenkins Children's Hospital research lab on 2nd floor. [name] will collect patient samples and separate plasma into coded tubes without other identifiers and place in -80 freezer. [name] will analyze these coded specimens in her lab with [name], discarding when samples are spent in the assay or at end of study, when all samples have been analyzed.
7. We will monitor for emesis with NAC administration, though we expect none with n.g. administration. All infants who have not achieved oral feeds have n.g. tubes through which the remainder of the feeds are given.

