- If parents wish to withdraw the infant from the study they may do so at any time, but they may not withdraw from the study procedures and still receive treatment as our outcomes depend on these tests in this very small sample size. We also have limited funds for NAC and cannot afford to continue to pay for the drug and treat without collecting our outcome variables. We may still collect outcome data, but the infant will not continue to receive treatment if the parent wishes to withdraw.

Statistical analysis and power analysis:

3. **Increase in daily po feeding volumes:** Our existing IDM cohort (n=9) had increase of 1.3 ± 1.7 ml/kg/d over 10 days before taVNS, vs 7.0ml/kg/d during taVNS in responders (including the 1 IDM responder). Even with this small sample, 4 IDM responders would allow us to detect a significant difference between prior to and during NAC+taVNS (power 80%, $\alpha = 0.05$, paired t-test).
4. **Number of IDM achieving full oral feeds:** If 6 out of 10 IDMs achieve full oral feeds with NAC+taVNS, we will determine a significant difference in response rate vs taVNS alone (1/9 responders) by χ^2 analysis.
5. **Secondary dMRI outcomes,** using our existing IDM cohort, we expect FA change/week in left PTR (0.031 ± 0.003) in NAC+taVNS responders vs our IDM taVNS (0.016 ± 0.003) requiring 3 in each group, or 8 IDMs for FA change/wk in CC (0.028 ± 0.004 NAC+taVNS vs 0.02 ± 0.006 taVNS alone) with $\alpha = 0.05$, 80% power, t-test (G*Power 3.1).

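### The rule that 6/10 vs 1/9 full oral feeds is significant by χ² holds only for the uncorrected test in a table with small expected counts; the plan should name one two-sided exact test

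*Combined protocol and SAP*

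**What the plan says.** The Study Endpoints section of the combined protocol and SAP lists this comparison among the primary outcome variables: "We will also compare categorical number of infants who achieve full oral feeds and avoid a G-tube in this group". The comparator is the "prior IDM cohort who only received taVNS and were largely non-responders (8/9"), that is, 1 responder in 9.

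Under Data Management, item 2 of the statistical and power analysis sets the target result: "If 6 out of 10 IDMs achieve full oral feeds with NAC+taVNS", then "we will determine a significant difference in response rate vs taVNS alone (1/9 responders) by χ^2 analysis". Item 4 of the later section headed Statistical analysis and power analysis repeats the rule.

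Neither item mentions a continuity correction, an exact test, sidedness or a significance level. A level of 0.05 is given for the feeding-volume and dMRI items only.

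**The concern.** The named method is a large-sample test, applied to 19 infants of whom 7 would be responders. Two questions follow. Does the declared significance depend on which form of the test is run? And does the test hold its nominal error rate at these group sizes?

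Both the uncorrected and the continuity-corrected statistics are called χ². If they disagree at 6/10, the plan's wording allows opposite verdicts on a primary outcome at the one result for which the rule was written. The pilot is meant to inform a larger trial application, so a disputed p-value would carry forward.

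**Working it through.** **Inputs.** New cohort: 10 infants (Number of Subjects), 6 responders assumed (item 2). Prior cohort: 9 infants, 1 responder (item 2, consistent with Study Endpoints). Two-sided α=0.05 is my assumption for this item.

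| | Full oral feeds | Not | Total |
|---|---|---|---|
| NAC+taVNS | 6 | 4 | 10 |
| taVNS alone | 1 | 8 | 9 |
| Total | 7 | 12 | 19 |

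**Expected counts** (row total × column total / 19):
- Responders: 10×7/19 = 3.68 and 9×7/19 = 3.32.
- Non-responders: 10×12/19 = 6.32 and 9×12/19 = 5.68.

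Two of the four are below 5.

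**The plan's own claim, uncorrected Pearson.** X² = N(ad−bc)²/(product of the four margins) = 19×(6×8−4×1)²/(10×9×7×12) = 19×44²/7560 = 4.866 on 1 df, p=0.027. The claim reproduces.

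**Continuity-corrected.** X² = 19×(44−19/2)²/7560 = 19×34.5²/7560 = 2.991, p=0.084.

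**Fisher, two-sided.** With margins fixed there are C(19,7) = 50,388 arrangements. Those no more probable than the observed one have 6, 7, 1 or 0 responders in the new cohort, with 1890, 120, 840 and 36 arrangements. The sum is 2886/50,388 = 0.057.

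**Unconditional exact tests, with 10 and 9 as the fixed group sizes.** Boschloo: the largest one-sided tail over the common response rate is 0.01626, doubled to 0.033. Barnard (pooled statistic): 0.028. Orientation matters in software. If the table is entered so that the responder totals 7 and 12 are treated as the fixed sizes, Boschloo's p comes out as 0.041, which is not the p-value for this design.

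**Threshold against a fixed 1/9.** At 5/10, Pearson gives p=0.069 and Fisher 0.141. At 7/10, Fisher gives 0.020 and continuity-corrected χ² 0.033. So the smallest significant count is 6/10 under Pearson and Boschloo, and 7/10 under Fisher and corrected χ².

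**True size of uncorrected χ².** For each common response rate, I summed the Binomial(10)×Binomial(9) probabilities of all outcomes with p<0.05:

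| Common rate | 1/9 | 20% | 30% | 40% | 50% (maximum) |
|---|---|---|---|---|---|
| Size | 2.8% | 5.3% | 5.9% | 6.2% | 6.5% |

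The maximum size by the same enumeration is 4.9% for Boschloo and 2.1% for Fisher.

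**One infant not evaluable (illustration).** For 5/9 vs 1/9, Pearson X² = 18×(5×8−4×1)²/(9×9×6×12) = 4.00, p=0.046. Boschloo gives 0.057 and Fisher 0.131.

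**The case against.** The strongest reply is that the plan is right. Its statement is arithmetically true for Pearson, and the exact Barnard p-value (0.028) is almost the same as Pearson's (0.027). With 10 infants against the fixed 1/9, Pearson and Boschloo reach the same decision at every possible count. Fisher's maximum size of 2.1% shows that it is strongly conservative here. All of this stands. A reader who sees only the Fisher and continuity-corrected results might infer that exact analysis overturns 6/10, or that the plan miscalculated. Neither follows.

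A reader might also infer that the type I error is inflated throughout. It is not. At 1/9, the only response rate the documents report for this population on taVNS alone, the size is 2.8%. It exceeds 5% at common rates of 20% and above, and by at most 1.5 percentage points.

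It can also be said that the intended version is inferable, since only uncorrected χ² makes 6/10 significant. That is fair as a reading, but the rule should not have to be worked out from its answer, and nothing in the text binds the analyst to it.

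The nine-infant case is hypothetical. The plan allows withdrawal at any time but says that outcome data may still be collected afterwards. Finally, this is a pilot meant to estimate an effect size. That lowers the stakes, but the plan still makes a significance claim on a primary outcome, and makes it twice.

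**Conclusion.** The point holds in a limited form. At the plan's own target result, the two tests called χ² fall on opposite sides of 0.05 (0.027 and 0.084), half the expected counts are below 5, and the uncorrected version can exceed a 5% error rate, up to 6.5%. The claim for 6/10 survives Boschloo and Barnard, so the defect is an unspecified approximate test and not a false threshold. If an infant is lost, the approximation could matter: at 5/9 vs 1/9, uncorrected χ² would declare significance where Boschloo and Fisher would not.

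This rests on two-sided testing at 0.05, which the plan does not state for this item. The size calculation also treats both cohorts as binomial samples with a common rate, although the 1/9 is already observed. The matter should be fixed; it is not a fatal flaw.

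**What to change.** In items 2 and 4, replace "by χ^2 analysis" with one named two-sided exact test at α=0.05, fixed before the data are analysed. Either option works:

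- **Boschloo's test**, with the two cohort sizes (10 and 9) as the fixed margins. The 6/10 threshold stays, with p=0.033 and a maximum size of 4.9%.
- **Fisher's exact test**, with the threshold restated as 7/10 (p=0.020) and the claim for 6/10 removed.

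No extra data are needed. With Boschloo the cost is a slightly less favourable p-value (0.033 instead of 0.027). With Fisher it is a harder target: at a true response rate of 60% and with 1/9 fixed, the chance of reaching the threshold falls from 63% (6 or more of 10) to 38% (7 or more of 10).

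### Emesis and bradycardia are safety outcomes with no planned off-treatment comparison, and the one check on the cause of emesis (a held dose) is too weak to settle it

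*Combined protocol and SAP*

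**What the plan says.** The Study Endpoints section lists the safety outcomes as "Gastric intolerance/emesis; bradycardia with taVNS (HR <80bpm for 5 seconds", with no baseline, comparator or analysis. In the same section, the primary outcome has a within-infant contrast, "comparing volumes before taVNS, to volumes during treatment within group". The statistical text, which appears under Data Management and again after Withdrawal of Subjects, covers feeding volume, full oral feeds and FA change. It does not mention safety.

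The Detailed Management Protocol sets the observation windows:

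- **Before NAC (step 1):** a baseline MRS and a blood sample only.
- **NAC (step 2):** every 6 hours, "administered 1h before a feed, for a total of 14 days".
- **Dilution (step 3):** the "bedside nurse will dilute the dose with sterile water 1:3 prior to NG administration".
- **Emesis (steps 2 and 7):** watched for alongside dosing. Step 7 reads "We will monitor for emesis with NAC administration, though we expect none with n.g. administration".
- **Frequent emesis (step 4):** "we will dilute in a greater volume of saline (1:4) and hold a dose to make sure emesis is not due to NAC". The step names reflux as the alternative cause. It does not define frequent or state the order of the hold and the re-dilution.
- **Heart rate (step 10):** the 80 bpm criterion is applied during taVNS feeds. A separate check looks for a brief fall and recovery when the perceptual threshold is set.
- **taVNS (steps 8 and 11):** starts on NAC day 4, two feeds a day for 14 days, and may be extended. NAC is not extended.

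The note to exclusion criterion 5 says: "Infants are on cardiorespiratory monitors through the nursery stay with recording devices to capture events and play them back".

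**The concern.** A count of events on treatment does not show whether treatment raised the infant's own rate. Step 4 shows that the investigators expect a competing cause of emesis, but its answer rests on what happens when a dose is withheld from an infant who is already vomiting often. A quiet interval could lead staff to blame NAC for reflux. If emesis then settles on the re-diluted doses, the new volume, the new diluent and natural variation are all possible reasons.

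For bradycardia, the two heart-rate observations in step 10 do not supply a comparison. The threshold check is tied to stimulation, but it is a different measure and is not made during feeding. On and off periods within a taVNS feed cannot serve either, because stimulation follows sucking and stops at pauses, so the two change together.

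The pilot is meant to inform a larger trial, and the inclusion criteria are said to be those of the planned phase II trial. If events occur, that trial would inherit counts that cannot be assigned to NAC, to taVNS or to the infants' background.

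**Working it through.** The plan gives no event rate, sample size or power for either safety outcome, so there is no figure to reproduce. The schedule figures below come from the protocol. All event rates are assumptions.

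**Schedule (steps 2, 8 and 11).** taVNS runs from day 4 to day 4 + 14 − 1 = 17, and NAC from day 1 to day 14. The phases are therefore:

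- NAC alone: days 1–3.
- Both: days 4–14 (11 days).
- taVNS alone: days 15–17 (3 days, or 3 × 4 = 12 six-hour intervals), plus any extension.

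Emesis monitoring is tied to NAC dosing, so none is specified for days 15–17. taVNS feeds number 2 × 14 = 28 per infant, or 280 in 10 infants.

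**What one held dose can show.** Let p be the chance of emesis per dose interval when NAC has no effect, with intervals independent. One held dose is then emesis-free with probability 1 − p, and 12 intervals off NAC are all emesis-free with probability (1 − p)^12.

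| Assumed p | One held dose emesis-free | 12 intervals all emesis-free |
|---|---|---|
| 0.1 | 0.90 | 0.28 |
| 0.2 | 0.80 | 0.07 |
| 0.3 | 0.70 | 0.01 |
| 0.5 | 0.50 | <0.001 |

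Emesis during the hold would point away from NAC, but that too is a single observation.

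**What phase counts could show for emesis.** The 95% limits on a rate ratio are the estimate times or divided by exp(1.96 × √(φ × (1/E0 + 1/E1))). E is infant-days times the daily rate, and φ is 1 (Poisson) or 2 (twofold overdispersion). With 10 infants there are 140 NAC infant-days, 110 with both treatments and 30 with taVNS alone. Two, 4 or 7 usable pre-NAC days (assumed) give 20, 40 or 70.

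| Comparison | φ | 0.2/day | 0.5/day | 1/day |
|---|---|---|---|---|
| 2 pre-NAC days vs NAC | 1 | 2.85 | 1.94 | 1.60 |
| | 2 | 4.40 | 2.55 | 1.94 |
| 4 pre-NAC days vs NAC | 1 | 2.19 | 1.64 | 1.42 |
| | 2 | 3.04 | 2.02 | 1.64 |
| 7 pre-NAC days vs NAC | 1 | 1.90 | 1.50 | 1.33 |
| | 2 | 2.48 | 1.78 | 1.50 |
| taVNS alone vs both | 1 | 2.47 | 1.77 | 1.50 |
| | 2 | 3.58 | 2.24 | 1.77 |

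Example: 4 pre-NAC days at 0.5/day with φ = 1 gives E0 = 20 and E1 = 70. Then √(1/20 + 1/70) = 0.2535, and exp(1.96 × 0.2535) = 1.64.

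**Bradycardia.** Step 10 reports none in the prior study, and step 9 says the taVNS protocol is unchanged from the existing cohort. If those 9 infants had 28 feeds each (assumed; 252 feeds, taken as independent), the chance of no event at 1% per feed is 0.99^252 = 0.08. Rates well above 1% are therefore hard to reconcile with the earlier experience. At 1%, comparing 280 taVNS feeds with 280 to 840 other oral feeds (2 to 6 a day, assumed) gives factors of 5.2 to 3.9 by the same formula with φ = 1. If no event occurs, the one-sided 95% upper limit is 1 − 0.05^(1/280) = 1.1% per feed with independent feeds, or 1 − 0.05^(1/10) = 26% of infants.

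**The case against.** This is an open, single-group pilot of 10 infants. Reporting events on treatment is usual at this stage, and the bradycardia outcome is defined that way. No stopping rule or comparative safety claim depends on attribution. Step 7 expects no emesis, and bradycardia was not seen before, so there may be nothing to attribute. The documents do not say how many oral feeds take place outside the two taVNS feeds, so that comparator may be thin or absent. The remark that such events are common concerns preterm infants, whereas these infants are beyond 39 weeks and stable at enrolment.

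Most of this stands, and it limits the priority. It does not remove the point about emesis. Step 4 offers a way of deciding cause, and that way is unreliable in exactly the infants in whom emesis is frequent.

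Two stronger readings are tempting:

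- **The change of diluent confounds the held dose itself.** It does not. Nothing is instilled when a dose is held, so volume and diluent cannot explain that interval. They affect only later doses. The order is not stated, and the text does not rule out a repeated hold.
- **Bradycardia will be common enough for a precise comparison.** The only evidence in the documents points the other way, and at 1% per feed the comparison is very imprecise.

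**Conclusion.** The point holds as a gap in attribution, mainly for emesis. Neither safety outcome has a planned pre-treatment or off-treatment comparison, and the single conditional check cannot carry the conclusion that step 4 draws from it. If NAC had no effect, one held dose would still be emesis-free 50% to 90% of the time, for assumed background rates of 50% down to 10% per interval.

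A reader might infer that safety cannot be assessed at all, or that the efficacy conclusions suffer. The documents support neither. On-treatment counts still bound the event rates, and the efficacy sample size is untouched. For bradycardia the gap matters only if events occur.

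The size of the gain rests on background rates that the documents do not give. Priority is low to moderate.

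**What to change.** **Emesis (main change).** Count emesis per day over the available pre-NAC days on which the infant was already eligible and in this unit. Continue by phase: NAC alone (days 1–3), both (days 4–14), taVNS alone (days 15–17 and any extension). Report within-infant differences descriptively, with each infant's number of pre-NAC days. If gastric intolerance is to include signs other than emesis, name them and count them in the same way. Keep the held dose as bedside management rather than as the rule for deciding cause, and report every held dose and dilution change.

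**Bradycardia (secondary).** Arrange in advance that the monitors capture heart rate below 80 bpm for 5 seconds and that recordings are kept. The protocol says events can be captured and played back, not that they are retained. Set any event in a taVNS feed against same-day or pre-treatment oral feeds without taVNS, where these exist. If no event occurs, report the count and its upper limit.

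**Cost.** Extraction from nursing records (assumed available) and an arrangement to keep recordings. No new procedure and no change to care are needed.

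**Downside.** The comparisons stay descriptive. A two-sided sign test needs at least 6 discordant infants, all in one direction (2 × 0.5^6 = 0.031; with 5, 2 × 0.5^5 = 0.0625). They are partly confounded with time, and same-day feeds may carry over effects of an earlier taVNS feed. Some infants will have few or no pre-NAC days; the inclusion criteria mention "some infants transferred into tertiary care centers".
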